3.3.1. Rationale for Selection of dose, and treatment schedule in the study

The dose proposed in this study, OXERVATE[™] 0.002% (20 mcg/mL) cenegermin-bkbj ophthalmic solution (one drop in each eye six times daily for 8 weeks), was tested in the previous NK studies (NGF0212 and NGF0214).

The 20 μ g/ml concentration of OXERVATETM 0.002% (20 mcg/mL) cenegermin-bkbj ophthalmic solution is well sustained by the current manufacturing process and is the commercial formulation currently approved and available in the USA.

The dose and route of administration of OXERVATETM 0.002% (20 mcg/mL) cenegermin-bkbj ophthalmic solution selected in this study is based on the approved marketed concentration as an eye drop approved for the treatment of NK.

Given the nature of the disease, an eight week treatment period at 6 doses/day is considered sufficient time to produce a reversal of PED in a Stage 2 and Stage 3 (more severe) NK patient population and reaches the maximal response in terms of efficacy as seen in up to 72% (REPARO) of patients who had complete corneal healing defined as absence of staining of the corneal lesion and no persistent staining in the rest of the cornea after 8 weeks of treatment. An established safety profile exists with cenegermin $20 \,\mu g$ /mL having been evaluated in six prior clinical trials. Additionally, toxicology and data showed cenegermin to be well tolerated in animal models with no systemic or ocular toxicity.

Patients with tolerability issues or worsening of symptoms may be discontinued at any time during the study.

4. SELECTION OF STUDY POPULATION

Adult males and females with Stage 1 NK (as defined in the inclusion criteria) will be included. A total of 35 evaluable patients (those patients completing 8 weeks of OxervateTM) are planned to be enrolled.

4.1. INCLUSION CRITERIA

To be eligible for inclusion into this study, each patient must fulfil the following inclusion criteria:

- 1. Male or female aged \geq 18 years.
- 2. Patients with Stage 1 NK defined by the Mackie criteria (Appendix 4)
- 3. Patients with Stage 1 NK characterized by all the following:
 - a. superficial punctate keratopathy (SPK) as shown by fluorescein corneal staining (FCS) equal to a grade 3 within the central zone using the National Eye Institute (NEI) scale (Appendix 4).

AND

- b. evidence of decreased corneal sensitivity (≤ 4 cm using the Cochet-Bonnet aesthesiometer) in the central qualifying zone of staining.
- 4. No improvement in NEI zone score between the Screening Visit (Visit 1) and Treatment Visit (Visit 2) for the qualifying zone determined at Visit 2.
- 5. Have a best corrected distance visual acuity (BCDVA), using corrective lenses if necessary, in the study eye, of at least +1.0 Log MAR (Snellen $\le 20/200$) if the clinician attributes the vision loss to the epithelium and the loss is not related to the macula in the affected eye(s).
- 6. The same eye (eligible eye/study eye) fulfills all the above criteria on the day of Screening (Visit 1) and again on Visit 2.
- 7. Patients with punctal occlusion or punctal plugs inserted prior to the study are eligible for enrollment provided that the punctal occlusion is maintained during the study period. If a punctal plug falls out during the study, it must be reinserted within 7 days.
- 8. Patients who are at high risk of progression or have a history of Stage 2 or Stage 3 NK per the Mackie classification.
- 9. Patients who have only one functional eye can be included if they meet all the criteria above and per the investigator's discretion are proper candidates to designate the one functional eye as the study eye.
- 10. Only patients who satisfy all Informed Consent requirements may be included in the study. The subject and/or his/her legal representative has read, signed, and dated the IRB approved Informed Consent document before any study-related procedures are performed.
- 11. Patients must have the ability and willingness to comply with study procedures.

4.2. EXCLUSION CRITERIA

Patients who meet any of the following criteria are NOT eligible for inclusion in the study.

- 1. In the opinion of the Investigator, there is evidence of an active ocular infection (bacterial, viral, protozoal) in either eye.
- 2. Use of non-diagnostic (e.g., topical drops used for clinical testing/evaluations) medications that can induce corneal toxicity between Visit 1 and Visit 2.
- 3. In the opinion of the investigator, have current or history of conditions that may confound the study data including but not limited to Ocular Cicatricial Pemphigoid (OCP), Graft Versus Host Disease (GVHD), neuromyelitis optica, uncontrolled dry eye, and Steven Johnson's syndrome.
- 4. History of severe systemic allergy or severe ocular allergy (including seasonal conjunctivitis expected during the subject's participation in the trial) or chronic conjunctivitis and/or keratitis other than dry eye disease.
- 5. Intraocular inflammation defined as Tyndall score >0.
- 6. Patients with severe vision loss with no potential for visual improvement in the study eye in the opinion of the investigator, or if the subject is deemed legally blind.
- 7. Patients with active severe blepharitis and/or severe meibomian gland disease who in the opinion of the investigator will require routine treatment during the study or have required routine treatment within 2 weeks of the study treatment visit (Visit 2). (This includes the use of doxycycline within 2 weeks prior to the treatment visit (Visit 2) for active MGD.)
- 8. History of any ocular surgery (including eyelid surgery and cataract surgery) within the three months before study treatment (Visit 2) and for Lasik or refractive surgical procedures within 3 months before study treatment (Visit 2). (An exception to the preceding statement is allowed if, in the opinion of the investigator, the ocular surgery is deemed the cause of the NK).
- 9. Ocular surgery or elective ocular surgery expected during participation in the trial.
- 10. Prior surgical procedure(s) for the treatment of NK including but not limited to tarsorrhaphy, conjunctival flap, the exception is for amniotic membrane transplantation. Enrollment of patients previously treated with amniotic membrane transplantation is allowed two weeks after the membrane has fully disappeared within the area with removal of any sutures or two weeks from removal of the Prokera ring before study treatment visit (Visit 2).
- 11. Treatment with Botox (botulinum toxin) injections in the study eye, used to induce pharmacologic blepharoptosis within 60 days prior study treatment visit (Visit 2).
- 12. Anticipated need to use therapeutic contact lenses or contact lens wear for refractive correction during the study treatment period in the Study Eye.
- 13. Patients with unstable medical condition that may confound the study data in the opinion of the investigator including but not limited to diabetes, thyroid disease, autoimmune disease, Parkinson's disease, and Multiple Sclerosis. Stable conditions managed with oral or injectable medications can be included, if per the investigators discretion the patient is not anticipated to have flare ups that could affect the ocular surface.
- 14. Patients with eyelid abnormality that may alter eyelid function including but not limited to Blepharospasm, Cerebrovascular accident, entropion, ectropion, floppy lid syndrome.

- 15. Use of glaucoma drops within 14 days prior to study treatment visit (Visit 2) and for the duration of the study. Patients can use oral Diamox during the study to control IOP.
- 16. Pregnant or lactating at study entry or who are planning a pregnancy.
- 17. Premenopausal female not using a medically acceptable form of birth control (abstinence, oral contraception, intrauterine device, surgically sterilized).
- 18. History of drug addiction or alcohol abuse documented within the past 5 years.
- 19. Participation in a clinical trial with a new active substance 14 days prior to study treatment visit (Visit 2). Per the investigator's evaluation that the participation in another clinical trial for an ocular surface product does not have residual effects on the ocular surface beyond 14 days prior to treatment that could confound the data by having an effect on staining.
- 20. Participation in another clinical trial study at the same time as the present study.
- 21. Participation in a Neurotrophic Keratitis study during the past 60 days prior to study treatment visit (Visit 2).
- 22. Are an employee of the site that is directly involved in the management, administration, or support of this study or be an immediate family member of the same.
- 23. Prior failure with treatment for Stage 1, 2 or 3 NK with OXERVATE[™] 0.002% (20 mcg/mL) cenegermin-bkbj ophthalmic solution. Failure defined as non-responder or lack of efficacy.

4.3. SELECTION OF STUDY EYE

The study eye is the eye at Visit 2 having Grade 3 FCS per the NEI scale in the central zone and a decreased corneal sensitivity (≤ 4 cm using the Cochet-Bonnet aesthesiometer) in the central zone at both Visit 1 and Visit 2. If both eyes have a qualifying central zone meeting FCS and corneal sensitivity requirements at both Visit 1 and Visit 2, the right eye will be selected as study eye.

Note: If both eyes meet the FCS and corneal sensitivity requirements in the central zone, the subject will be treated bilaterally. If only one eye qualifies, but the contralateral eye has FCS in the central zone ≥2 on NEI scale and the Investigator feels that both eyes would benefit from treatment (i.e. the qualifying eye is abnormal, but does not meet criteria for study) both eyes may be treated with study product. Data will be collected and recorded in the eCRF for both eyes throughout the study.

If there is only one qualifying eye/one study eye, only one eye will be treated; however, both eyes will be evaluated, and data will be collected for both eyes.

4.4. ASSIGNMENT OF SUBJECT NUMBER

Each patient who is screened to participate in this study will be assigned a unique 6-digit PID number (e.g. 001101) consisting of a 3-digit study center number followed by the 3-digit screening number assigned sequentially by each study center.

[figure not shown]

5. STUDY PRODUCT

5.1. PRESENTATION, STORAGE, PACKAGING AND LABELING OF THE STUDY PRODUCT

5.1.1. Presentation of Study Product

The Study Product will be provided as the commercially available OXERVATE[™] 0.002% (20 mcg/mL) cenegermin-bkbj ophthalmic solution. The patient will receive 1 or 2 biweekly cartons sufficient for two weeks of dosing at Visit 2, Visit 3, Visit 4, and Visit 5. The patients will be provided with enough pipettes and adaptors to be used for the administration of the Study Product. The subject will receive a total of 56 (or 112 for bilateral treatment) OXERVATE[™] 0.002% (20 mcg/mL) cenegermin-bkbj ophthalmic solution vials over the 8-week duration of the study product treatment, 1 OXERVATE[™] 0.002% (20 mcg/mL) cenegermin-bkbj ophthalmic solution vial to be used per day. The patient will pick up Study Product from the Investigator's office and bring back used vial for reconciliation at the subsequent study visit.

5.1.4. Description of Study Product

Study Product is OXERVATETM 0.002% (20 mcg/mL) cenegermin-bkbj ophthalmic solution. OXERVATETM 0.002% (20 mcg/mL) cenegermin-bkbj ophthalmic solution is a sterile perservative-free ophthamic solution containing 0.002% (20 mcg/mL) of rhNFG drug substance.

Each vial contains 1.0 ml of solution.

Commercially available artificial tears will be supplied to patients in the study by the sponsor. Study sponsor will provide SYSTANE® Preservative-Free Original Lubricant Eye Drops to be used up to four times per day as needed during the screening period, and as needed for rescue therapy and during the follow-up period.

5.2. DOSE, ROUTE AND SCHEDULE OF PRODUCT ADMINISTRATION

Both OXERVATE[™] 0.002% (20 mcg/mL) cenegermin-bkbj ophthalmic solution (study product) and SYSTANE Original[®] (to be used for the screening and follow-up periods only) are to be used in this study and are for topical ocular usage only.

The Study Product will be dosed one drop (35 μ l- .70 μ g of cenegermin-bkbj/drop) 6 times a day in the affected eye(s) for 8 weeks of treatment. The timing of instillation should be adjusted if a patient's awakening and/or bedtime differs based on the suggestion above in Table 1 Dosing Schedule. An example of Dosing Instructions is also provided in the Manual of Procedures (MOP).

Instructions for First Dose:

Patients will be instructed to self-administer the study product one drop in the affected eye(s) six times a day at 2 hour intervals starting on the day after Visit 2 (Day 0-Baseline and First Study product Pick Up) of the treatment period. On Day 1, the patient will start the first dose following Table 1 Dosing Schedule. *The patient should not start therapy on the same day as Day 0/Visit 2.*

On the day of Visit 3/Week 2 (For Study Product Pick-Up), the Study Product dosed is to be instilled in the clinic by the patient at approximately 2 hours intervals according to their established daily schedule for self-administration of the study product at home and the Study Product should be taken from the kit which is dispensed at the visit. This to ensure the patient does not miss a dose during the drop off and pick up day.

Systane Original[®] (commercially available preservative free artificial tears provided by sponsor) will be used only as strictly needed during the Screening and Follow up periods. The use of Systane Original[®] will be clearly documented in the patient's study dosing diary and in the eCRF.

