2. SCHEDULE OF EVALUATIONS

	Visit 1	Visit 2	Visit 3	Visit 4	Visit 5	Visit 6	Visit 7
	Day	Day 0	Day 14	Day 28	Day 42	Day 56	Day 224
	(-14)	(±2)	(-2)	(-2)	(-2)	(-4)	(±7)
	Week -2		Week 2	Week 4	Week 6	Week 8	Week 32
Procedures	Screening	Baseline	Product Pick-Up	Treatment Follow-Up	Product Pick-Up	End of Treatme nt	Follow-up/ End of Study
ICF/HIPAA	X						
Demographics, Systemic and Ocular Medical History	X						
Collect date of Stage 1 NK initial diagnosis	X						
Pregnancy Test	X	X				X	
Record AEs	X	X	X	X	X	X	X
Concomitant Medications	X	X	X	X	X	X	X
IDEEL		X		X		X	X
EQ-5D-5L		X		X		X	X
BCDVA	X	X		X		X	X
External Ocular Examination	X	X		X		X	X
Slit Lamp Examination	X	X		X		X	X
Corneal Photography Without Fluorescein	X	X		X		X	X
TFBUT		X		X		X	X
FCS (NEI Scale)	X	X		X		X	X
Corneal Photography with Fluorescein	X	X		X		X	X
Corneal Sensitivity Testing	X	X		X		X	X
Schirmer Test (w/o Anesthesia)		X		X		X	X
IOP	X	X				X	X
Anterior Segment OCT (selected sites)		X				X	X
Confocal microscopy (selected sites)		X				X	X
Inclusion/Exclusion Criteria	X	X					
Assigned to Treatment		X					
Product Dispensation		X	X	X	X		
Collect Used/Unused Study Product			X	X	X	X	
AT Dispensation	X	-				X	
Dispense Daily Dosing Diary	X	X	X	X	X	X	
Evaluate Daily Dosing Diary			X	X	X	X	
Evaluate AT Use- in patient daily diary		X					X

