3.3. OVERALL STUDY DESIGN

This clinical study will be a multi-center, open label, prospective study of 8 weeks of treatment with 24 weeks of follow-up to evaluate the safety and efficacy of OXERVATE[™] 0.002% (20 mcg/mL) cenegermin-bkbj ophthalmic solution administered as one drop in the affected eye(s), 6 times per day at 2-hour intervals, for eight weeks in patients with Stage 1 Neurotrophic Keratitis (NK).

The study is divided into four phases as follows:

- 5. Screening Visit (Day -14): Procedures for inclusion will be performed at both Visit 1 (Screening) and Visit 2 (Baseline). Commercially available artificial tears (AT) provided by the sponsor will be permitted during the Screening period as needed up to four times a day.
- 6. Washout period (from day minus 14 to day 0): 14 days with no further treatment except commercially available preservative-free artificial tears provided by the sponsor. (Note: Xiidra™ and Restasis™ use is disallowed for 14 days prior to Visit 2.) Artificial tears (AT) provided by the sponsor will be permitted up to four times a day and will be tracked via daily diary during washout period.

7. **Treatment:**

- a. Treatment (weeks 1-8): eligible patients will start OXERVATE[™] 0.002% (20 mcg/mL) cenegermin-bkbj ophthalmic solution administered as one drop in the affected eye(s), 6 times per day at 2-hour intervals, for eight weeks. During the treatment period, only study product will be permitted for topical ocular treatment. *Commercially available preservative free artificial tears (AT) provided by Sponsor are not allowed during the treatment period.*
- 8. **Follow up (weeks 9-32):** For the 24 weeks post treatment:
 - a. For patients completely healed, no treatment is allowed except for commercially available AT provided by the Sponsor, administered at the physician's discretion. The use of artificial tears will be tracked via a daily dosing diary.
 - b. For patients not completely healed and who don't meet criteria for premature discontinuation, will also be followed up but any treatment is allowed at the discretion of the physician. All treatment will be tracked as concomitant medications.

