Rescue Therapy: Commercially available preservative free artificial tears (AT) provided by Sponsor are not allowed during the treatment period. Per the investigator's discretion if the patient requires rescue therapy during the 8-week treatment period then they can receive artificial tears provided by the sponsor for up to four times per day. The frequency of rescue therapy must be documented in the patient's diary.

The study will be a total of 34 weeks in duration: a screening period of 2 weeks, followed by 8 weeks of treatment and a 24-week follow-up period. At the end of the screening period (at Visit 2), patients meeting the entry criteria for this study will be assigned to treatment with OXERVATE[™] 0.002% (20

mcg/mL) cenegermin-bkbj ophthalmic solution which will be known as Study Product beginning the morning following Visit 2.

Following the completion of the treatment period, patients will be followed up for an additional 24 weeks (for patients healed and non-healed [and not meeting d/c criteria] at Week 8) and will be evaluated at the end of the follow-up period. At the investigator's discretion, the subject may be seen for an Unscheduled Visit to evaluate for safety. Patients who prematurely discontinue for whatever reason will not be followed post discontinuation and should have Visit 6 assessments completed.

At Visit 1, eligible patients will be instructed to discontinue all topical ophthalmic medications and will only be allowed to use commercially available preservative free tears provided by the sponsor to be used up to four times per day during the screening period. At the conclusion of the Baseline Visit (Visit 2) eligible patients will be dispensed a 2-week supply of Study Product from the onsite freezer in a sealed bag and will be instructed to self-administer the Study Product one drop six times a day starting on the day after Day 0/ Visit 2 through Week 8 of the controlled treatment period according to the dosing schedule shown in Table 1 (Dosing Schedule).

Table 1 Dosing Schedule

TREATMENT	TREATMENT DOSING SCHEDULE*
OXERVATE™ 0.002% (20 mcg/mL) cenegermin-bkbj ophthalmic solution	Morning (8 AM)
	Mid-morning (10 AM)
	Noon (12 PM)
	Early afternoon (2 PM)
	Mid afternoon (4 PM)
	Late afternoon (6 PM)

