5.3.1. Prior and concomitant medications

As a general rule, no ophthalmic medication other than Study Product and concomitant Study Product (Systane[®] -artificial tears provided by Sponsor) will be given to the patient from the screening day until all the final study evaluations have been completed. Systane[®], provided by the Sponsor, may be used *during screening and the follow up only*.

All medications (including over-the-counter drugs, systemic medications, herbal products, vitamins, and antacids) should be documented at screening and also taken within 14 days of study treatment Visit 2 and throughout the study will be clearly documented on the Concomitant Medications eCRF page.

Medication entries should be specific to product name (if a combination drug product) and spelled correctly. The dose, unit, frequency, route of administration, start date, discontinuation date, and indication should also be recorded. For medications administered only one time, the frequency column may reflect "once."

D Dompo	
Table 3 Medications and Procedures	Minimum Washout Period Prior to Treatment (Visit 2)
Have had incisional ocular surface surgery (e.g., LASIK, refractive, pterygium removal).	90 days
Ocular surgery (including eyelid surgery or cataract surgery)	90 days
Botox (botulinum toxin) injections in the study eye.	60 days
Any Investigational Product for NK	60 days
Any Investigational Product applied to the ocular surface if per the investigators discretion the investigational product does not have residual effects on the ocular surface that can confound the data	14 days
Topical ocular or systemic antibiotics for the treatment of an ocular condition	14 days
Topical cyclosporine (all doses and formulations)	14 days
Lifitegrast	14 days
Glaucoma topical medications (Use of Diamox orally during the study is acceptable)-Investigator should ensure stable IOP before/by Visit 2	14 days
Topical ocular corticosteroids, ocular non-steroidal anti- inflammatory drugs (NSAIDs), and topical dermatologic corticosteroids on the face within 14 days prior to Visit 2 and during study participation	14 days
Topical ocular antihistamine and/or mast cell stabilizers within 14 days prior to Visit 2. Have used topical ocular vasoconstrictors for the purpose of eye whitening within 14 days prior to Visit 2 (phenylephrine used to dilate the eyes is allowed).	14 days

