6.2. EARLY WITHDRAWAL FROM STUDY

A premature discontinuation will occur when a patient who signed the ICF ceases participation in the study, regardless of circumstances, before the completion of the study protocol procedures. Patients can be prematurely discontinued from the study for one of the following reasons:

- Progression from Stage 1 to Stage 2 or Stage 3 NK, or corneal melting/perforation
- At the PI discretion patient is considered to be a non-responder (no improvement from baseline).
- In the qualifying/Study Eye, the FCS is unchanged (Grade=3) from baseline after 8 weeks of treatment in the qualifying NEI zone or there is an increase in FCS ≥1 within a non-qualifying NEI zone in the same eye.
- Decrease in BCDVA by >10 ETDRS letters
- Onset of infection (bacterial or viral)
- Protocol violation, including lack of compliance defined as <80% of doses taken based on diary documentation between treatment clinic visits.
- Withdrawal of consent
- Lost to follow-up during the treatment period (Every effort must be made to contact the patient; a registered letter must be sent)
- Study terminated by the Sponsor
- Other reasons, such as administrative reasons or pregnancy
- Development of AE or unacceptable toxicity per the investigator's discretion, precluding further therapy with the study drug.
- Severe protocol violations, such as an incorrect treatment administration, or a concomitant use of not permitted medications. Before removal, these cases should first be discussed with Dompé.

The reasons for premature discontinuation from the study will be reflected on the Study Termination Record of the CRF. For patients who prematurely discontinue, Visit 6 procedures will be completed, and these patients will be considered off study and will no longer be followed.

For patients that discontinue prematurely, the investigator should refer patients for further treatment as appropriate.

Replacement Procedures

Patients in this study who prematurely discontinue before completion of 8 weeks of treatment with OxervateTM will be replaced. Patients prematurely discontinuing during follow up treatment will not be replaced.

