5 ANALYSIS OF EFFICACY

5.1 Primary Efficacy Variable

The primary efficacy variable is the achievement of epithelial healing at Visit 6/Week 8, which is defined as Grade 1 or absence of staining (Grade 0) in the central qualifying zone of study eye via FCS (per NEI scale). The primary efficacy variable will be summarized as a binary goal attainment variable (Yes/No).

The primary analysis will be based on observed cases (i.e. no missing data imputation). As a sensitivity analysis, the last post baseline observation prior to Week 8 will be carried forward for imputing missing data at Week 8. In addition the worst post baseline observation prior to Week 8 will be carried forward for imputing missing data at Week 8 and patients who took any rescue medication prior to Week 8 will be considered as a treatment failure (not epithelial healed) at Week 8.

All summaries and analyses for the primary efficacy variable will be presented for both FAS and FTS populations.

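### Artificial tears during treatment are barred in some sections and allowed as rescue in others; no rescue supply is scheduled, and Protocol 6.2 leaves the status of rescued patients open

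*Protocol*

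**What the plan says.** **Text that bars tears during treatment.**
- Protocol 5.2: "to be used for the screening and follow-up periods only".
- Protocol 5.3.1: "during screening and the follow up only".
- Protocol 3.3, treatment paragraph: "Commercially available preservative free artificial tears (AT) provided by Sponsor are not allowed during the treatment period", with no exception given there.
- The synopsis and 3.3 both also state that, from Visit 2, sponsor tears will not be used while study product is taken.
- Protocol 6.1.2 has site staff remind the patient at Visit 2 that Systane is not allowed during treatment.

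**Text that allows tears as rescue.**
- Protocol 3.3, Rescue Therapy: at the investigator's discretion, "if the patient requires rescue therapy during the 8-week treatment period then they can receive artificial tears provided by the sponsor". The synopsis and SAP 1.3.2.2 have the same provision.
- The treatment paragraph of the synopsis adds the rescue exception that its counterpart in 3.3 lacks.
- Protocol 5.1.4 supplies tears "as needed for rescue therapy and during the follow-up period".

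**Schedule (Protocol 2).** Tears are dispensed at Visits 1 and 6 only. The row "Evaluate AT Use- in patient daily diary" is marked at Visits 2 and 7 only. The general diary review is marked at Visits 3 to 6, and concomitant medications at every visit.

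**Consequences.** Protocol 6.2 lists "a concomitant use of not permitted medications" as an example of a severe protocol violation for which a patient can be discontinued, after discussion with the sponsor. Patients who discontinue before completing 8 weeks of treatment are replaced. In a sensitivity analysis of the primary variable, SAP 5.1 states that "patients who took any rescue medication prior to Week 8 will be considered as a treatment failure".

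**The concern.** A site that follows 5.2, 5.3.1 and the Visit 2 instruction would treat tears taken in the treatment period as a breach. A site that follows the Rescue Therapy paragraph would treat the same use as permitted. Section 6.2 does not settle it, because it never says whether tears given as rescue count as non-permitted medication.

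Three things depend on the answer.
- **Retention.** A patient discontinued for tear use leaves the Full Treated Set, which SAP 2.6.4 restricts to patients treated through Visit 6. That set is one of the two on which SAP 5.1 reports the primary variable. The patient is also replaced.
- **Supply.** A site that accepts rescue has no scheduled visit at which to dispense it.
- **Data.** The rescue-as-failure analysis is only as good as the record of rescue use. A rescue that goes unrecorded leaves the patient's observed result standing.

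The issue bears on the main endpoint because Protocol 2.1 itself lists preservative-free artificial tears as part of Stage 1 care.

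**Working it through.** **1. Permission, side by side**

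| Place | Tears during treatment |
|---|---|
| Protocol 5.2 | Screening and follow-up only |
| Protocol 5.3.1 | Screening and follow-up only |
| Protocol 3.3, treatment paragraph | Barred, no exception |
| Synopsis and 3.3, text on use from Visit 2 | Not used |
| Protocol 6.1.2, patient instruction | Barred |
| Synopsis, treatment paragraph | Barred except as rescue |
| Synopsis and 3.3, Rescue Therapy; SAP 1.3.2.2 | Barred, then allowed as rescue at the investigator's discretion |
| Protocol 5.1.4 | Supplied for rescue |

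A general rule with a rescue exception fits the last three rows. It does not fit the word *only* in 5.2 and 5.3.1.

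**2. Supply.** Protocol 6.1.1 tells patients to bring their tears back at Visit 2, and 6.1.2 collects them there. The next dispensing mark is at Visit 6, so none falls within the treatment period.

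**3. Capture and reporting.** The tear-specific review row is blank at Visits 3 to 6. Rescue frequency must nevertheless be entered in the diary (3.3), the diary is reviewed at those four visits, and concomitant medications are recorded at each. On the reporting side, the SAP's dedicated tear-use summaries cover washout (4.3) and follow-up (5.3) only. Appendix 2 of the SAP lists no summary table of rescue use during treatment.

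**4. The plan's own precision figure.** Protocol 9.1 gives lower 95% limits of 40% and 54% for n = 35 at 58% and 72% healed. The exact lower limit is the 0.025 quantile of Beta(x, n − x + 1) with x = np:
- x = 35 × 0.58 = 20.3 gives 40.2%.
- x = 35 × 0.72 = 25.2 gives 54.3%.

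Both figures reproduce, and this point does not dispute them.

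**5. Illustration for the Full Treated Set, before replacement.** The documents give no rescue rate, so the number rescued is an assumption. Take N = 35 and H = 25 healed at Week 8, the whole number nearest to 25.2. If k rescued patients are removed, of whom h had healed, the rate is (H − h)/(N − k).

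| Handling | Rate | Exact 95% CI |
|---|---|---|
| All kept | 25/35 = 71.4% | 53.7 to 85.4 |
| k = 3, all healers | 22/32 = 68.8% | 50.0 to 83.9 |
| k = 5, all healers | 20/30 = 66.7% | 47.2 to 82.7 |
| k = 3, no healers | 25/32 = 78.1% | 60.0 to 90.7 |
| k = 5, no healers | 25/30 = 83.3% | 65.3 to 94.4 |

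Removing healers lowers the rate by 3 to 5 points. Removing non-healers raises it by 7 to 12. After replacement, the result would also depend on how the replacement patients fare.

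**The case against.** **The wording can largely be read as rule plus exception.** The synopsis puts both in one sentence, the Rescue Therapy paragraphs put both in one place, and 5.3.1 opens as a general rule. The Visit 2 instruction could be aimed at self-directed use, leaving investigator-directed rescue intact. This narrows the conflict but does not remove it: 5.2 and 5.3.1 restrict use without exception, and the schedule has no dispensing step for rescue.

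**A reader might infer that rescue use goes unreviewed or that the data will be missing.** The documents do not support that. Diary entry is mandatory, the diary is checked at Visits 3 to 6, and 5.2 calls for Systane use to be entered in the eCRF as well. The SAP tabulates ocular concomitant medications and lists tear use and tear accountability. What is lacking is a tear-specific check and a dedicated treatment-period summary.

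**A reader might infer that rescued patients are removed routinely and vanish from the analysis.** That does not follow either. Under 6.2 patients *can* be discontinued, the ground concerns severe violations, and such cases go to the sponsor first. Anyone dosed stays in the FAS and has Visit 6 procedures completed at discontinuation. SAP 5.1 also plans carried-forward analyses for a missing Week 8 value, and Appendix 2 lists both on the FAS.

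**A reader might take the gap between counting rescued healers as healed and as failures for an effect of the contradiction.** With 3 to 5 rescued healers that gap is 25/35 (71%) against 22/35 to 20/35 (63% to 57%). It is the difference between the SAP's primary analysis, which has no rescue rule, and a sensitivity analysis that counts rescue as failure. Both are prespecified.

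**Tears alone may explain little healing.** They were allowed up to four times daily in washout, and inclusion criterion 4 requires no improvement in the qualifying zone over that period. This limits the effect of tears on the endpoint but does not exclude it.

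**Conclusion.** The point holds as a contradiction with practical consequences. The protocol both bars and allows sponsor tears during treatment, schedules no supply for the use it allows, and does not say in 6.2 how that use is classed. Two patients with the same rescue use could be handled differently, one kept and the other discontinued and replaced, although sponsor discussion before removal reduces that risk.

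The numerical effect is confined to the Full Treated Set. On the assumption of 25/35 healed and 3 to 5 rescued patients removed, the rate before replacement lies between 67% and 83%, against 71% if all are kept. Its direction depends on whether those removed had healed. These figures illustrate sensitivity and do not predict the result.

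For the rescue-as-failure analysis, a route for the data exists but lacks a tear-specific check at Visits 3 to 6. The SAP plans no dedicated summary showing how many patients that analysis reclassifies. The matter should be corrected, but it does not invalidate the primary analysis or the stated precision.

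**What to change.** 1. Reconcile the synopsis, 3.3 (treatment paragraph, Rescue Therapy paragraph and the text on use from Visit 2), 5.1.4, 5.2, 5.3.1, the Visit 2 instruction in 6.1.2, and SAP 1.3.2.2 to one statement. This review does not say which rule is right.
2. Add one sentence to 6.2 saying whether tears given as rescue count as non-permitted medication.
3. If rescue is retained, mark tear dispensing as needed during treatment, and mark the existing tear-use review row at Visits 3 to 6.
4. If rescue is retained, also add to the SAP a summary of treatment-period rescue: number of patients, frequency, and Week 8 healing status of those rescued.

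The cost is a protocol clarification, a few marks in existing schedule rows, a short extra check at visits where the diary is already reviewed, and one further table.
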